Due to the high cost of sugammadex, some researchers have hypothesized that a lower dose is required when combined with neostigmine. A 2015 study from Beirut in adults undergoing elective surgery demonstrated that a dose of 2 mg/kg of sugammadex combined with neostigmine 0.05 mg/kg was non-inferior to the standard dose of 4 mg/kg of sugammadex in reversing deep NMB, defined as returning from a TOF count of 0 to a TOF ratio of 0.9 within 5 minutes, with similar times to extubation as well as no cases of recurarization in the post anesthetic care unit (PACU) (16). Lobaz, Sammut and Damodaran reported in 2013 the use of sugammadex as rescue therapy for a 71-year-old patient with end stage renal disease who was unable to be weaned off the ventilator almost five hours after receiving a single 1.2 mg/kg dose of rocuronium. He had initially achieved a TOF of 4, was reversed with 2.5 mg of neostigmine 45 minutes after induction, but failed to maintain adequate spontaneous ventilation despite his TOF remaining at 4, and was transferred to the intensive care unit 3 hours post induction. There, his TOF steadily declined to 2, as a result of which he received a 6 mg/kg dose of sugammadex, causing him to be successfully extubated ten minutes later (17). It is similarly important to dose sugammadex appropriately; Carollo et al. published a case report in 2019 of an 8-month-old patient who had recurarization after a 4 mg/kg dose of sugammadex was given with a TOF count of 2/4, which fortunately resolved after a second 4 mg/kg dose of sugammadex (18).

Lastly, known common adverse effects of neostigmine include bradycardia, nausea and vomiting (19), while the use of sugammadex has been found to lead to nausea, vomiting, hypotension and headache in \geq 10% of patients (5). There have also been case reports of marked bradycardia possibly leading to cardiac arrest with the use of both agents.

Page 6 of 30 Version: 3 (10/14/2024)

4. Study Endpoints

Primary study outcome:

The time taken to achieve a TOF ratio of 0.9 after the use of the intervention drug versus placebo in a patient population that has already received neostigmine for NMB reversal.

Secondary study outcome:

The percentage of patients who achieve a TOF ratio of 0.9 within 1 minute, 2 minutes, 5 minutes, and 10 minutes.

Safety outcomes:

The incidence in PACU (measured in %) of:

- i. Nausea,
- ii. Vomiting,
- iii. Bradycardia²,
- iv. Tachycardia³, and
- v. Hypotension⁴.

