These patients will be randomized using the Emory University REDCap (Research Electronic Data Capture) software to six groups: 2 mg/kg (the lowest dose approved by the FDA), 1 mg/kg, 0.5 mg/kg, 0.25 mg/kg, 0.125 mg/kg of sugammadex and placebo. Doses would be based on actual body weight. The time taken to reach a TOF ratio of 0.9 thereafter would be measured. If the patient fails to achieve this goal by 10 minutes, sugammadex would be given in 2 mg/kg increments until the patient reaches this threshold and can be safely extubated. The TOF ratio would be measured again at 30 minutes after arrival at the PACU to exclude delayed residual NMB with the plan to give further 2 mg/kg doses of sugammadex if detected.

The inclusion of a placebo group would allow us to examine if patients may recover spontaneously over that time without needing any sugammadex at all, and what parameters may predict that subset of patients. It will also improve the dose response modelling, in that randomization has been weighted so that patients who are least likely to need sugammadex (i.e. if they achieved a TOF count of 4 twitches without fade) are more likely to be in the placebo group or at the lowest dose of sugammadex that is being tested.

The time taken to a TOF ratio of 0.9 after the intervention drug has been given would be compared for statistically significant differences, controlling for the:

- TOF count (3 twitches, 4 twitches with fade, 4 twitches without fade), and
- TOF ratio (0 to < 0.9)

15 minutes after neostigmine has been given and prior to giving the intervention drug.

Quantitative neuromuscular monitoring will be carried out using electromyography, which measures the TOF ratio every 20 seconds. The TOF count (between 0 to 4) and the TOF ratio (0 to 1) would be measured and recorded at baseline and after administration of the study drug. If the TOF ratio remains < 0.9 after this, or if the patient exhibits any symptoms or signs of residual NMB blockade, a further 2 mg/kg dose of sugammadex would be given until the patient achieves a TOF ratio of 0.9.

Page 8 of 30 Version: 3 (10/14/2024)

7. Statistical Analysis Plan

Power Analysis

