An *a priori* power analysis was conducted using G*Power 3.1.9.4 (20). We used an ANOVA F-Test for one-way omnibus difference between groups, alpha threshold of 0.05 for rejecting the null hypothesis, statistical power of 0.80 and a "very large" effect size of 0.765 was calculated based on results from a 2013 randomized controlled trial that examined time from TOF count = 4 to TOF ratio 1.0 comparing neostigmine to three different doses of sugammadex: 0.5, 1.0, and 2.0 mg/kg (15). This gave a required sample size of N=24. This number was increased to N=36 to account for patients with poor modeling from a high starting TOFR (resulting in few data points for that patient) or incomplete recovery within the maximum ten minutes allotted. An anticipated 70% of those enrolled will become ineligible because of an initial TOFR of 90% or greater, thus not requiring any medications, so up to 120 patients may need to be recruited and screened, but only 36 will receive any treatment.

Methodology

Randomization will occur with permuted block randomization, divided into 18 groups, to ensure proportional allocation of participants in each group over time. Dose randomization will be assigned after stratifying by initial TOFC, with a set number of patients recruited for each group, as seen the table below. This ensures that patients who likely need a lower dose are more likely to receive it. Randomization will not occur until participation is assured, i.e., their TOFR is <0.90.

Table 1: Randomization plan for patients (n=36)

| Sugammadex Dose (mg/kg) → | | 0.00 | 0.125 | 0.25 | 0.50 | 1.00 | 2.00 | | | |
|---------------------------|-----------------|------|--|----------|------------|---------|---------|------|-------|----|
| Initial TOFR | Initial TOFC | Fade | placebo | | | | | | Total | |
| ≥ 0.9 | NA | NA | No treatment; track for adverse events | | | 0 | | | | |
| | | 4 | No | 3 pt | 3 pt | 2 pt | 2 pt | 1 pt | 1 pt | 12 |
| < 0.9 | 4 | Yes | 2 pt | 2 pt | 2 pt | 2 pt | 2 pt | 2 pt | 12 | |
| | 3 | NA | 1 pt | 1 pt | 2 pt | 2 pt | 3 pt | 3 pt | 12 | |
| < 0.9 | 0-2 | NA | No t | treatmen | t; track f | or adve | se even | ts | 0 | |
| Total # of Patients (pt) | | | 6 | 6 | 6 | 6 | 6 | 6 | 36 | |

Statistical Methodology

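### Section 6 gives two rescue rules that disagree on timing, and nothing in the plan separates recovery due to rescue from recovery on study drug

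*Combined protocol and SAP*

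**What the plan says.** Section 6 states the first rule directly after describing randomization: "If the patient fails to achieve this goal by 10 minutes, sugammadex would be given in 2 mg/kg increments". The second comes at the end of the section, in the paragraph on neuromuscular monitoring. That paragraph describes "electromyography, which measures the TOF ratio every 20 seconds", says that count and ratio "would be measured and recorded at baseline and after administration of the study drug", and continues: "If the TOF ratio remains < 0.9 after this, or if the patient exhibits any symptoms or signs of residual NMB blockade". In that case a further 2 mg/kg is given.

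The endpoints in section 4 depend on what happens in those minutes. The primary outcome is "The time taken to achieve a TOF ratio of 0.9 after the use of the intervention drug versus placebo". The secondary outcome is the percentage reaching 0.9 "within 1 minute, 2 minutes, 5 minutes, and 10 minutes". Section 7 sets a success criterion of 95% of patients at 0.9 or above by 5 minutes, judged from a regression of TOF ratio on time. It mentions "incomplete recovery within the maximum ten minutes allotted" as one reason for raising the sample size from 24 to 36.

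Section 7 does not mention rescue. The data list in section 20 has the time of study drug (hours and minutes) and the time to 0.9 (seconds), but no field for a rescue dose or its time.

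**The concern.** Every efficacy result is meant to describe recovery on the assigned dose alone. Section 6 includes the placebo arm to show whether patients recover in that period with no sugammadex. If rescue can be given before 10 minutes, a slow patient's 0.9 may be reached on the rescue dose and recorded as the study-drug time.

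Blinding does not protect against this, because slow recovery is itself the trigger. The patients affected would be mainly those on placebo and the lowest doses. Two things could follow: the difference between doses shrinks, and low doses look more adequate than they are. The second would favour the hypothesis in section 2 that a dose below the labelled one is enough.

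**Working it through.** **1. The plan's only power figure.** Section 7 gives N=24 from a one-way ANOVA with f = 0.765, alpha 0.05 and power 0.80. Using the noncentral F distribution with noncentrality N·f², four groups (the number in the cited 2013 trial) give a balanced N of 24 with power 0.82, so the figure reproduces. With the six randomized groups, power is 0.70 at N=24 and 0.92 at N=36. The point below does not rest on these numbers.

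**2. The two rules side by side.**

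| | First rule | Second rule |
|---|---|---|
| Trigger | Ratio 0.9 not reached | Ratio below 0.9, or any symptom or sign |
| Earliest time | 10 minutes after study drug | None stated; the sentence before it refers only to the period after study drug |
| Mention of the 10-minute limit | Yes | No |

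The ten-minute window in section 7 supports reading the ratio trigger as a 10-minute rule. It does not settle when the symptom trigger may act.

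**3. What the literal reading would allow.** One reading every 20 seconds gives 10 × 60 / 20 = 30 readings by 10 minutes, of which 29 fall before the 10-minute mark. The second rule excludes none of them.

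**4. Which recorded results would change.** Assume that 0.9 is reached 1.8 minutes after a rescue dose. Section 3 gives this as the mean after 2 mg/kg, from a TOF count of 4 to a ratio of 1.0, in a different setting. Recorded time = rescue time + 1.8 minutes.
- Rescue by 5 − 1.8 = 3.2 minutes is recorded as recovery within 5 minutes.
- Rescue by 10 − 1.8 = 8.2 minutes is recorded as recovery within 10 minutes.
- Rescue at 10 minutes gives 11.8 minutes. The 5- and 10-minute percentages are untouched, but 11.8 could still enter the primary outcome, since no rule excludes it.

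**5. Direction, under assumed inputs.** Assume placebo recovery is lognormal with median M between 10 and 30 minutes and log-SD 0.5. The true share recovered by time t is Φ[(ln t − ln M)/0.5].
- By 10 minutes: Φ(0) = 50% at M = 10, and Φ(−2.20) = 1.4% at M = 30.
- By 5 minutes: Φ(−1.39) = 8% at M = 10, and about 0% at M = 30.

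If every unrecovered patient were rescued at 5 minutes, the recorded 10-minute share would be 100%. If all were rescued at 2 minutes, the recorded 5-minute share would be 100%. These are extremes, not forecasts.

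**6. Effect on the dose comparison, also assumed.** The four mean times quoted in section 3 (8.5, 4.1, 2.1 and 1.8 minutes) have SD 2.68, so f = 0.765 implies a common SD of 2.68 / 0.765 = 3.50. Take six arm means of 8.5, 8.5, 6.3, 4.1, 2.1 and 1.8. The neostigmine mean stands in for the two slowest arms, and 6.3 is midway between 8.5 and 4.1. Capping the slow means imitates early rescue.

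| Cap on arm means | f | Power at N=36 |
|---|---|---|
| None | 0.79 | 0.94 |
| 8 minutes | 0.73 | 0.89 |
| 6 minutes | 0.52 | 0.57 |
| 5 minutes | 0.39 | 0.34 |

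The direction is clear. The true position in this range is unknown, because no document gives a frequency or timing of early rescue.

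**The case against.** The strongest reply is that the second rule is only a loose restatement of the first. With a reading every 20 seconds, applying it literally would rescue almost every unrecovered patient at once and would defeat the later time points and the placebo arm. Sections 4 and 7 both work with a 10-minute horizon. The symptom clause may also concern patients after extubation, in line with the recheck 30 minutes after PACU arrival, when time to 0.9 is already known.

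Much of this stands. A reader might infer that the protocol intends early rescue; the documents do not support that, and the 10-minute reading of the ratio trigger is the more natural one. But the second rule contains neither the 10-minute limit nor a restriction to the PACU, and the anesthesia provider works from section 6.

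A reader might also infer that early-rescued patients will be counted as recovered. No text says so. Handling is simply unspecified, and section 7 treats incomplete recovery by ten minutes as a loss that the larger sample absorbs.

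Finally, one patient in a group of six is 1/6 = 16.7 percentage points. That is the weight of any single patient, whatever the issue, and not an estimate of this bias.

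**Conclusion.** The concern holds as an unreconciled inconsistency with a missing analysis rule. Section 6, as written, permits rescue inside the endpoint window. If that happened, the time-to-0.9 field would record recovery due to rescue, and nothing in sections 7 or 20 would identify it. The likely direction is faster apparent recovery in the placebo and low-dose arms and a smaller dose effect. This assumes that some patients are rescued early, that they are mostly the slow ones, and that readings after rescue are kept.

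The size cannot be computed from the documents; the figures above show direction and range only. One part does not depend on how the second rule is read: even with rescue at 10 minutes only, the plan does not say how a 0.9 reached after that rescue enters the primary outcome. The matter should be settled before the analysis.

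**What to change.** 1. **Protocol.** The investigators reconcile the two passages in section 6 on when, and on what trigger, rescue may be given. Which clinical rule applies is for them to decide. The analysis rules below work under either.
2. **Data list (section 20).** Add the dose and time of every rescue, timed from study drug in seconds, since one endpoint is at 1 minute. For patients already treated, these would have to come from the source charts that section 21 uses for checking case report forms; the documents do not say whether they are charted that precisely. The REDCap form may already hold them, but it is not in the documents.
3. **SAP (section 7),** for a patient rescued before the first reading of 0.9:
   - drop TOF ratios measured after rescue from the regression of ratio on time;
   - count the patient as not having reached 0.9 at every later time point (2, 5 and 10 minutes, as applicable) and for the 5-minute success criterion;
   - for time to 0.9, treat the patient as unrecovered through 10 minutes. Do not censor at the time of rescue: rescue depends on slow recovery, so that censoring would be informative.

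The cost is a wording amendment, one addition to the data form and a few SAP sentences. Reported recovery rates in the low-dose arms may come out slightly less favourable.

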- Prisoners
- Cognitively impaired or Individuals with Impaired Decision-Making Capacity
- Individuals who are not able to clearly understand English

Racial and ethnic classification of subjects would be collected from their electronic medical record (which is based on self-identification) for descriptive statistics. Race would comprise the following six categories: white, black or African American, American Indian or Alaska Native, Asian, Native Hawaiian or Other Pacific Islander, and two or more races. Ethnicity would be either Hispanic/Latino or not Hispanic/Latino. This information will not be used as a variable to explain differences between participants, but will be presented in Table 1 as part of the study's demographic data, which may help in assessing if the study could be generalized to other patient populations in turn.

The number of individuals who are not able to clearly understand English constitute a minority of the patient population at Grady Memorial Hospital.

13. Vulnerable Populations

N/A

14. Local Number of Participants

Up to 120 patients may need to be enrolled and screened, but only 36 will receive any treatment. We anticipate a similar percentage of participants according to sex, but the majority

Page 11 of 30 Version: 3 (10/14/2024)

⁵ Child-Pugh classification includes bilirubin, INR, albumin, ascites and encephalopathy. A total score of 5-6 is class A, 7-9 is class B and 10-15 is class C.

would likely be either white or black due to general patient demographics in Grady Memorial Hospital.

15. Recruitment Methods

All patients presenting to the anesthesia pre-admission clinic as well as inpatients scheduled for the operating room the next day would be screened via electronic medical record on a day-to-day basis to determine if they are eligible to participate in the study. Eligibility screening would be determined based on their most recent surgical notes (i.e. whether the patient would likely undergo general anesthesia as well as NMB).

Patients who are eligible would then be contacted and introduced to the study by a study team member for potential recruitment, at a minimum the day before the date of surgery in order to allow enough time for the patient to consider the risks and benefits of participation.

16. Withdrawal of Participants

Patients may be withdrawn from the research study without their consent if they are found to not meet the study's inclusion criteria, e.g.

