- Did not require general anesthesia for surgery,
- Did not require NMB,
- Did not receive neostigmine for NMB reversal,
- Had a TOF count < 3 or a TOF ratio ≥ 0.9 fifteen minutes after neostigmine, or
- Remained intubated in the immediate postoperative period.

As the study intervention is a one-time dose of the study drug in the OR, no further action should be required if the patient decides to later withdraw from the study. The study will be terminated when the number of participants has reached the required threshold.

17. Risk to Participants

The most common risks of sugammadex as listed by the FDA (5) include:

- Nausea (23-26%)
- Vomiting (11-15%)
- Pain (36-52%)

Uncommon but serious risks of sugammadex include:

- Hypotension (4-13%)
- Tachycardia (2-5%)

Page 12 of 30 Version: 3 (10/14/2024)

- Bradycardia (1-5%)
- Anaphylaxis (0.3%)

Notably, all of these are known to be risks of general anesthesia as well as surgery and are routinely monitored for and treated in the PACU.

18. Potential Benefits to Participants

All study subjects will have any residual NMB reversed, which will prevent any postoperative complications such as respiratory compromise or weakness.

19. Compensation to Participants

N/A

20. Data Management and Confidentiality

Data to be collected include:

- Baseline demographics: MRN, date of birth, sex (male/female), race (white, black, American Indian or Alaska Native, Asian, Native Hawaiian or Other Pacific Islander, two or more races), ethnicity (Hispanic or Latino, not Hispanic or Latino), weight (kg)
- ii. Preoperative details: ASA status (I-IV)
- iii. Surgery details: date of surgery, diagnosis, surgery, start case time (hr: min), end case time (hr: min)
- iv. Anesthesia details: if succinylcholine was used (Y/N), total amount of rocuronium given (mg), the last dose of rocuronium that was given (mg), the time that the last dose of rocuronium was given (hr:min), neostigmine dose (mg), the time that neostigmine was given (hr: min), the time that the study drug was given (hr: min).
- v. TOF ratio (0-1)
 - Before any paralytic is given at the start of the case
 - Before neostigmine is given at the end of the case
 - Before the study drug is given
 - 30 minutes after PACU arrival
- vi. TOF count (0-4 ± fade)
 - Before neostigmine is given at the end of the case
 - Before the study drug is given
- vii. The time taken to achieve a TOF ratio of 0.9 (seconds).

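### The recruitment figure of up to 120 is the expected number for 36 eligible patients in total, stated as a maximum, and it leaves no margin for chance, the 12-per-stratum quotas or other withdrawals

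*Combined protocol and SAP*

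**What the plan says.** The Power Analysis in Section 7 sets the treated number at 36, raised from a calculated 24 ("This number was increased to N=36 to account for patients with poor modeling from a high starting TOFR", or incomplete recovery within ten minutes). It then states: "An anticipated 70% of those enrolled will become ineligible because of an initial TOFR of 90% or greater". From this it concludes: "so up to 120 patients may need to be recruited and screened, but only 36 will receive any treatment". Section 14, Local Number of Participants, repeats it: "Up to 120 patients may need to be enrolled and screened, but only 36 will receive any treatment".

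The Methodology part of Section 7 does not accept any 36 eligible patients. It says: "Dose randomization will be assigned after stratifying by initial TOFC, with a set number of patients recruited for each group". Table 1 fixes 12 patients in each of three strata: TOF count 4 without fade, TOF count 4 with fade, and TOF count 3. Patients with a TOF ratio below 0.9 but a TOF count of 0 to 2 are not treated.

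Section 16 lists several grounds for withdrawal. One reads "Had a TOF count < 3 or a TOF ratio ≥ 0.9 fifteen minutes after neostigmine". The others are no general anesthesia, no neuromuscular blockade, no neostigmine, and continued intubation. The documents give no rate for any of these except the TOF ratio criterion. They give no expected stratum shares and no rule for a stratum that fills early or stays open.

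**The concern.** The wording makes an average look like an upper bound. It counts only one source of ineligibility, and it treats the target as 36 patients of any kind although the design needs 12 of each of three kinds. As Table 1 is written, a 13th patient in a full stratum has no cell to enter.

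At stake are the enrollment number under which the trial is approved and the dose balance in Table 1. Each dose reaches 6 patients only if all three strata fill. The cells are deliberately uneven: the TOF count 3 stratum supplies 3 of the 6 patients at each of 1.00 and 2.00 mg/kg, and the stratum with TOF count 4 without fade supplies 3 of the 6 on placebo and on 0.125 mg/kg. A short stratum would therefore deplete particular doses and thin the planned secondary analysis of dose by TOF count.

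**Working it through.** **Inputs from the documents.** Treated patients: 36 (Section 7). Ineligible because of TOF ratio: 70%, so at most 30% are eligible (Section 7). Stratum quotas: 12, 12 and 12 (Table 1).

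**Assumptions, because the documents give no figures.** Stratum shares among eligible patients: equal, 40/35/25 or 50/30/20. Other withdrawals: 0%, 10% or 20% of otherwise eligible patients.

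**1. The plan's figure.** 36/(1 − 0.70) = 36/0.30 = 120. It reproduces exactly and contains no margin.

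**2. Chance alone, ignoring strata.** Let X be the number eligible among 120, binomial with p = 0.30 and mean 120 × 0.30 = 36. Then P(X ≥ 36) = 0.53. Reaching 36 with 80% probability takes 134 patients, and with 90% probability 142.

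**3. With the stratum quotas.** Let X1, X2, X3 be the numbers eligible in each stratum among n patients, multinomial with cell probabilities 0.30 × share. The requirement is that all three reach 12. With equal strata each has mean 120 × 0.10 = 12, so each alone is close to an even chance and all three must succeed.

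| Stratum split | P(all filled by 120) | Mean n needed | n for 80% | n for 90% |
|---|---|---|---|---|
| Equal | 0.13 | 150 | 172 | 187 |
| 40/35/25 (assumed) | 0.075 | 168 | 198 | 220 |
| 50/30/20 (assumed) | 0.017 | 206 | 246 | 275 |

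Equal strata are the most favorable split, so at 30% eligibility about 0.13 is an upper bound whatever the true shares.

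**4. With other losses, equal strata.**

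| Other losses (assumed) | Eligible | Expected n for 36 in total | P(≥36 of 120) | P(all strata filled by 120) | n for 90% (strata) |
|---|---|---|---|---|---|
| 10% | 0.30 × 0.90 = 0.27 | 36/0.27 = 133.3, so 134 | 0.26 | 0.044 | 208 |
| 20% | 0.30 × 0.80 = 0.24 | 36/0.24 = 150 | 0.08 | 0.01 | 234 |

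**5. Size of the shortfall if recruitment did end at 120.** Places filled are the sum over strata of min(Xj, 12). At 30% eligibility and no other losses, the mean is 32.1 of 36 with equal strata and 29.1 with 50/30/20. The margin above the plan's 24 is 36 − 24 = 12 places, of which about 3.9 or 6.9 would be used. At least 24 places are filled with probability 99% and 96% respectively.

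**The case against.** A reader might infer that the trial will stop at 120 and miss its 36. The documents do not say so. Section 16 ends the study when the required number of participants is reached, and Sections 7 and 14 say only that up to 120 may be needed. Section 26 cites 20 to 30 suitable elective cases per weekday, so screening further looks feasible. This stands: the shortfall in step 5 is conditional on 120 being treated as the approved ceiling.

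A reader might also infer a wrong sum or a damaged analysis. Neither holds. The division is correct; the fault is using a mean as a maximum. Unfilled cells cost precision and balance but do not bias the estimates. Even at 120, the plan's calculated 24 (taken as stated) would very probably be exceeded. That is only partial comfort, because the extra 12 were meant for poor model fit and incomplete recovery, not for empty strata.

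Some of the Section 16 losses are reduced in advance. Section 15 screens records for likely general anesthesia and blockade, and Section 11 excludes anticipated postoperative intubation. Low TOF counts and omitted neostigmine remain, at unknown rates.

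Finally, the result is sensitive to eligibility. At the 39% residual-block rate that Section 3 cites for neostigmine in moderate block, the strata would fill by 120 with probability 0.64 (equal) or 0.16 (50/30/20). But that rate includes TOF counts of 1 and 2, and it is not the plan's assumption.

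**Conclusion.** The point holds as an error in the planned enrollment number, of modest severity. Two results rest on the plan's own 30% and Table 1 alone: a probability of 0.53 of reaching 36 in total by 120, and at most about 0.13 of filling all three strata. Any withdrawals beyond the TOF ratio criterion lower both. Every figure for a particular unequal split or loss rate is an assumption and should be read as a range. The consequence is for feasibility, the approved enrollment number and the balance of 6 per dose. The documents do not support a claim that the trial will stop short, or that its estimates would be biased.

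**What to change.** In Sections 7 and 14, replace the up-to-120 figure with two numbers: an expected number to be consented and screened, and an upper limit with a stated probability of filling all three strata. State the stratum shares and other losses assumed for each.

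- With equal strata and no other losses: about 150 expected and about 187 for 90% assurance.
- With equal strata and 10% other losses (assumption): about 208 for 90% assurance.
- With a 50/30/20 split and no other losses (assumption): about 275 for 90% assurance.

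The 150 and 187 should not be adopted without that context, since they are the most favorable case. Add a rule for an eligible patient who arrives after the stratum is full, and for a stratum still open when the upper limit is reached.

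The 36 treated stay unchanged. The cost is one amendment and more patients consented and screened who receive no study drug: 187 − 120 = 67 more at the limit in the most favorable case, and 275 − 120 = 155 more under the 50/30/20 assumption.
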